One method to attack these deficiencies in current program practice is to attack the time component of the hemostasis equation. In doing so, it is hypothesized that if radial artery compression time can be shortened to 40 minutes or less, the following could result: improved catheterization lab efficiency, greater patient satisfaction and lower complication rates, including RAO, may be improved. As concerns improved cath lab efficiency, a system that standardizes compression technique and shortens compression time to that which is fully under the supervision and care of cath lab holding room personnel, will also eliminate the variability of recovery staff needing to manage the hemostasis band / site, and complications typically associated with patient management being carried out in multiple settings within the hospital. To summarize, the potential advantages of a hemostasis system for PCI incorporating the benefits of the StatSeal technology used in combination with a hemostasis band as compared to a hemostasis band alone may include:

- Decreased radial artery compression times, aka Band In Place (BIP) time.
- Decreased incidence of RAO complications at discharge, or 24 hours, whichever occurs first
- Decreased incidence of other complications associated with TRA, such as hematoma, bleeding, and oozing.
- Elimination or reduction in the need for additional equipment, such as Doppler units, plethysmographs and pulse oximeters to assess hemostasis band efficacy
- Facilitate arterial site management to the more specialized catheterization lab staff/personnel that are better trained to recognize complications that occur during (BIP) band in place time.
- Decreasing the workload to the staff by virtue of shortened band in place times and improve procedural throughput.
- Facilitate greater patient comfort resulting from decrease band in place time and faster wound healing.

To do so, the effects of anticoagulation used during a PCI must be taken in to account.

II. DESCRIPTION OF THE STUDY DEVICE:

Recently, a new compound – potassium ferrate, in combination with a hydrophylic polymer which is formed in to a disc when compressed - has been used in conjunction with hemostasis bands to shorten compression times. This product (trade name StatSeal Advanced) is an FDA

approved product comprised of a topical hydrophilic polymer and potassium ferrate disc, [Photo 1] formed by compression of the compound.

Photo 1: StatSeal Advanced Disc

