When in the direct contact with even a small amount of blood, the compound forms an occlusive seal through simultaneous iron-mediated agglomeration of blood solids/proteins and rapid dehydration of the blood. Seal formation is independent of the clotting cascade, facilitating sealing regardless of anticoagulation / antiplatelet status of the patient. Following cessation of pressure being applied to the site, the remnants of StatSeal form what resemble a 'scab', and remains in place for 24 hours, covered with a band-aid or Tegaderm patch.

In clinical testing using a protocol refined at the University of Miami Miller School of Medicine, the use of this compound in conjunction with commercially available hemostasis bands has demonstrated the potential to significantly shorten the time required to achieve hemostasis^{11,12}. Further, these results demonstrated the ability to achieve hemostasis using StatSeal with similar, or fewer complications when compared to standard methods, and did so regardless of the patient's anticoagulation status.

INDICATION FOR USE

StatSeal Advanced is a commercially available product in the United States, and is indicated for use on patients in whom the radial artery has been used to gain vascular access for a cardiovascular procedure.

DEVICE STORAGE AND ACCOUNTABILITY

StatSeal Advanced is provided in a sterile, foil pouch to protect it from humidity / moisture. As with most medical products, it should be stored in a cool, dry, secure environment. StatSeal Advance will be provided at no charge by the manufacturer for use in the study.

Damaged devices will be returned to the manufacturer (Biolife, LLC, Sarasota,FL). All unused devices may be retained by the site for continued use, if they so choose.

III. STUDY OBJECTIVE(S)

The primary objectives of this study are to evaluate the performance of StatSeal Advanced used in conjunction with the TR Band (SSA) as compared to the TR Band without SSA (TRB) relative to:

1. the incidence of peri-procedural radial artery occlusion (RAO) at discharge or 24 hours, whichever occurs first, and;
2. the Time to Hemostasis (TTH)

HMS is defined as the Hemostasis Management System employed based on which group the patient is randomized to (either SSA or TRB).

Radial Artery Occlusion is defined as the absence of flow to the hand based upon plethysmography – pulse oximetry (Pleth-Ox) performed using the Barbeau scale.

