Time to Hemostasis (TTH) is defined as the time period required to achieve hemostasis, more specifically the time during which the subject is wearing the HMS system and the system is active, e.g. applying compressive force to the access site. For clarity, the time period that a HMS is left on the wrist while totally deflated is not considered as part of the TTH time.

IV. STUDY DESIGN AND METHODOLOGY

STUDY DESIGN

This study is a physician initiated, prospective, observational, two arm, randomized study to be performed at up to four experienced 'Radial First' centers. A minimum of 120 patients having undergone successful radial catheterization will be enrolled in the study, 60 in each arm.

Enrollment will continue at each site on discretion of the investigators until each center enrolls a minimum of 30 patients, or a maximum of 180 patients are enrolled. Clinicians will perform the catheterization in accordance with local standard practice, with a minimum of 5,000 units of unfractionated heparin for anticoagulation.

STUDY METHODS:

Patient Selection Criteria Study subjects will be identified in the catheterization laboratory holding area and asked to sign the informed consent prior to their catheterization procedure before the administration of sedative agents.

Inclusion Criteria:

- Patient undergoing diagnostic angiography or PCI via the radial artery
- Patients with a Barbeau test prior to the procedure showing pattern A,B,or C.

Exclusion Criteria:

Candidates for this study will be excluded if any **one** of the following criteria is true.

- Use of a radial sheath larger than 6 Fr (a 7Fr-in-6 Glidesheath Slender[®] is allowed).
- Use of an anticoagulant other than unfractionated heparin or bivalirudin.

- Any anticipated need for continued anticoagulation post-catheterization. Glycoprotein inhibitors are acceptable.
- Any active treatment with oral anticoagulants continued during course of procedure.
- Presence of arteriovenous dialysis fistula in the ipsilateral arm.
- Any physical deformity or trauma / injury of either wrist that would prevent proper placement or function of the hemostasis band.
- Raynaud's syndrome or known peripheral vascular disease of the forearm.
- Mental incompetence or inability to follow the instructions to complete the study.
- History or presence of Radial Artery Occlusion.
- Barbeau test showing Pattern D.
- Patients undergoing catheterization from the femoral or ulnar artery approach.

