2. A subject withdraws consent to participate. Patients who withdraw from the study will be replaced and excluded from data analysis.

[figure not shown]
Protocol:

Control patients: Patients will have a TR band applied over the arteriotomy site and inflated with 15-18ml of air. After aspirating and clearing the contents of the sheath, the radial sheath will be removed. The TR band will be deflated until bleeding occurs, and 2 ml of air will be reintroduced to provide hemostasis. Patent hemostasis will be documented with plethysmography and oximetry as described below within 5 minutes after band application and removal, and within 30 min of discharge or after 24 hours. The TR band will be left inflated and in place for 2 hours following the procedure for all patients (regardless of diagnostic or PCI procedure), after which deflation attempts will commence.

Statseal Protocol: Patients will have a Statseal Advance (SSA) disc applied after withdrawing the radial sheath 2-4 cm. A Tegaderm dressing will be applied to secure the disc position. The TR band will be applied over the SSA disc with the center of the balloon (the green dot) over the center of the SSA disc. The TR band will be inflated with 8cc of air (which is typically occlusive pressure), and the sheath removed. No deflation will occur immediately. After 20 minutes of pressure, 3 cc of air will be removed from the TR band. After an additional 20 minutes (40 minutes after procedure), the TR band will be completely deflated, and the TR band left in place. After an additional 20 minutes (60 minutes after procedure) the TR band will be removed.

[rest of page intentionally blank]

STUDY OVERVIEW GRAPHIC

V. STUDY ACTIVITIES & GUIDELINES

Inspection Prior to Use

Prior to initiating any study activities, inspect the HMS devices for any damage. Do not use any device that appears compromised or damaged.

Required Accessories for each experiment

- Hemostasis Band (TR Band, Terumo, Inc.)
- StatSeal Advanced disc (if randomized to test group)
- Pulse oximeter

ACTIVITIES AND ASSESSMENTS

Informed Consent:

Subjects must have read the contents of the written informed consent document, had all questions regarding the study adequately answered by study staff, and signed and dated the document prior to any study related activities. See Appendix 1 for a sample of the Informed Consent document.

Definitions of Baseline and Procedural Variables:

Smoking: Active smoking or >20 pack year tobacco history.

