The sample size of 120 patients is estimated to have 90% power to detect an average difference in time to removal of the TR band of 60 minutes between the SSA and TRB groups, using a relatively large standard deviation of 100 minutes and a two-sided alpha of 0.05.

Descriptive summary statistics will be presented for all study variables. Continuous variables will be displayed as means with standard deviations and medians with 75th and 25th percentiles. Categorical variables will be summarized as frequencies with their respective percentages with two-sided 95% exact confidence intervals of the percentages. Statistical comparisons for continuous variables will be performed using the Student's t test or Mann-Whitney U test, as appropriate. Comparisons for categorical variables will be performed using the Chi square test or Fisher exact test, as appropriate. A two-sided P value of 0.05 will be considered statistically significant.

Categorical variables will include, but are not limited to:

- Percent of patients in each arm with total TTH of 60 minutes or less.
- Percent of patients in each arm with TTH of 40 minutes or less without complication.
- The percentage of patients in each arm with bleeding, oozing or hematoma during TTH, further delineated by the EASY bleeding and hematoma classification attached.
- Percent of patients in each arm with RAO at each /all follow-up points.
- Percent of patients in each arm with radial patency as tested with Pleth-ox at each designated test time point.

Primary Efficacy Outcomes:

In each arm the:

- Total Time to Hemostasis (TTH), defined as the total time the HMS applies compressive force until successful hemostasis is achieved without complication.

Secondary Efficacy Outcomes:

In each arm the:

- Percent of patients free from radial artery occlusion at discharge or at 24 hours, whichever occurs first.
- Percent of patients with Barbeau test patterns A,B,C,D at initial application of the HMS
- Percent of SSA patients with Barbeau test patterns A,B,C,D after 20' of HMS time.
- Percent of patients with Barbeau test patterns A,B,C,D at full deflation of the HMS. (40' for SSA group; per protocol in the TRB group)
- Percent of patients with Barbeau test patterns A,B,C,D at discharge or at 24 hours, whichever occurs first.
- Percent of patients in whom successful hemostasis is achieved in one hour or less.

Primary Safety Outcome:

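### Bleeding counted during TTH and the TTH cut-offs are compared across scheduled compression of 40 min against at least 120 min, so those tests partly or wholly reflect the schedule

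*Protocol*

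**What the plan says.** **Schedules (Protocol IV, control and Statseal paragraphs).** Control (TRB): "The TR band will be left inflated and in place for 2 hours following the procedure for all patients", diagnostic and PCI cases alike, with deflation attempts starting only then. SSA: "After an additional 20 minutes (40 minutes after procedure), the TR band will be completely deflated", and "After an additional 20 minutes (60 minutes after procedure) the TR band will be removed".

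**TTH.** Protocol III counts time while the system is compressing the site and adds that "the time period that a HMS is left on the wrist while totally deflated is not considered as part of the TTH time". Protocol VI makes TTH the primary efficacy outcome, "defined as the total time the HMS applies compressive force until successful hemostasis is achieved without complication".

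**Categorical variables (Protocol VI).** The list includes, by arm, the share with TTH no longer than 60 minutes, the share with TTH no longer than 40 minutes and no complication, and the share with bleeding, oozing or hematoma while TTH is running. A secondary efficacy outcome is hemostasis within one hour, with no statement of how it is timed. Protocol VI plans chi-square or Fisher tests for categorical variables; the SAP compares discrete data by Fisher's test. Neither makes an exception for these items.

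**Safety outcomes (Protocol VI).** Access-site events, with class I/II hematoma secondary and class III to V primary, are counted up to discharge or 24 hours in both arms. The SAP models hematoma formation as a secondary outcome and does not restate a window.

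**Sample size (Protocol VI).** 120 patients give 90% power for a 60-minute mean difference in time to band removal, SD 100 minutes, two-sided alpha 0.05.

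**The concern.** Two kinds of analysis inherit the difference in schedule.

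First, an event counted only while TTH runs is counted for as long as the arm's band is inflated. With equal true bleeding, the arm with the shorter scheduled window records fewer events. An SSA bleed after the 40-minute deflation is missed unless it leads to re-inflation that extends TTH. At stake is a bleeding advantage for SSA that is partly an artefact of observation time.

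Second, a control patient treated to protocol cannot have a TTH of 40 or 60 minutes or less. A between-arm test on those cut-offs compares SSA with a zero fixed in advance, and its p-value carries no information about how quickly hemostasis occurs in the control arm.

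Two smaller matters follow from the same schedules: TTH cannot separate the disc from the schedule that comes with it, and the stated power is for band removal rather than for TTH.

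**Working it through.** **1. The plan's own figure.** Inputs from Protocol VI: difference 60, SD 100, two-sided 0.05, power 90%. Normal approximation: n per arm = 2 × (1.960 + 1.282)² × (100/60)² = 58.4, so 59. The t-based solution is 59.35, so 60 per arm and 120 in total; power at 60 per arm is 90.3%. The stated figure reproduces.

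**2. Schedule arithmetic (Protocol III and IV).**

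| | SSA | TRB | Scheduled gap |
|---|---|---|---|
| Compression counted in TTH | 40 min | at least 120 min | at least 80 min |
| Band removal | 60 min | not before 120 min | at least 60 min |

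These are gaps between scheduled times under adherence. The observed gap can be smaller if SSA compression has to be prolonged. The 60-minute design effect equals the smallest scheduled gap in band removal.

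**3. Bleeding counted during TTH.** Assumptions, none of them in the documents: the same constant bleeding rate in both arms, 60 per arm, Fisher's test at two-sided 0.05. Let p be the incidence by 120 minutes and q the share of SSA bleeds between 40 and 120 minutes that are counted because re-inflation extends TTH.

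- Counted in TRB: p.
- Counted in SSA with q = 0: s = 1 − (1 − p)^(40/120). For p = 0.20, s = 1 − 0.80^(1/3) = 0.072.
- In general SSA counts s + q(p − s).

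Summing the two binomial distributions over all tables where Fisher's test is significant with fewer events in SSA gives the chance of a false result favouring SSA:

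| p by 120 min | s | q = 0 | q = 0.5 | q = 1 |
|---|---|---|---|---|
| 2% | 0.7% | 0.1% | 0.1% | <0.1% |
| 5% | 1.7% | 3% | 1.3% | 0.5% |
| 10% | 3.4% | 16% | 4.4% | 1.1% |
| 20% | 7.2% | 44% | 10% | 1.4% |
| 30% | 11.2% | 66% | 16% | 1.5% |

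The q = 1 column is what a common 120-minute window would give. The constant rate matters too: if bleeding were concentrated in the first 40 minutes, the windows would differ little in effect.

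**4. Cut-offs.** TRB on schedule is 0/60 for TTH of 40 minutes or less and for 60 minutes or less. Against 0/60, Fisher's p is 0.119 for 4/60 in SSA, 0.057 for 5/60 and 0.027 for 6/60. Six SSA patients below the cut-off are enough for significance, whatever TRB hemostasis is like before 120 minutes. At 4/60 the mean expected count is 2 per arm, so Fisher is the relevant test.

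**5. Power for TTH.** With 60 per arm and an 80-minute difference, t-based power is 99.1% if the SD is 100, 95.2% if 120 and 82.6% if 150. The SD for TTH is an assumption; the plan states 100 for band removal only.

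**The case against.** **The named safety outcomes already have a common window.** This stands. Protocol VI counts access-site events, including every hematoma class, to discharge or 24 hours in both arms. That is also the natural reading of the SAP's secondary hematoma outcome, although the SAP would be clearer if it said so. A reader might infer that the trial's safety comparison as a whole is biased; the documents do not support that. Only the listed variable tied to TTH is affected, and it is not a designated primary or secondary outcome.

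**Later SSA bleeds may be counted after all.** This has force. TTH is "defined as the total time the HMS applies compressive force until successful hemostasis is achieved without complication", so a bleed at deflation may mean that TTH has not ended, which moves q towards 1. The protocol gives no re-inflation rule and does not settle the point. The 44% and 66% figures are therefore worst cases.

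**This is a trial of two regimens.** Also right. The Clinical Need section asks what follows "if radial artery compression time can be shortened to 40 minutes or less" and describes "a system that standardizes compression technique and shortens compression time"; both schedules are stated openly. A reader might infer that the TTH comparison is invalid, or that a gap of 80 minutes is guaranteed even with an inert disc. Neither follows: the regimen comparison is legitimate, and the observed gap depends on bleeding times that the documents do not give. What remains is a limit on attribution, since TRB hemostasis before 120 minutes is never assessed.

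**A 0% beside an openly stated two-hour schedule misleads nobody.** Partly fair for an attentive reader, but both documents would still attach a p-value to it.

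**The common window is not perfectly common.** True. It ends at discharge or 24 hours, whichever comes first, and the protocol expects shorter compression to speed discharge. Minor oozing after deflation is not named among the safety outcomes and may not meet the adverse event definition, which requires additional risk and care. The fix has to deal with both.

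**Conclusion.** The concern holds within limits.

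- **Bleeding during TTH:** compared over scheduled windows of 40 minutes against at least 120, a ratio of at least 3. The direction favours SSA if some bleeding comes after 40 minutes and is not captured by re-inflation. The size cannot be fixed from the documents: from negligible at 2% to 5% bleeding to substantial at 20% to 30% with no later SSA bleeds counted, and no inflation if all are counted. This rests on the assumed constant and equal rate.
- **TTH cut-offs:** 0% in TRB under adherence, so a between-arm p-value reflects the schedule. The same applies to hemostasis within one hour only if it is timed by TTH, which the protocol does not say.
- **Minor:** TTH supports a conclusion about disc plus schedule against band plus schedule, not about the disc alone. Power is stated for band removal. A reader might infer that the trial is too small for TTH; nothing in the documents shows that, and at the stated SD the scheduled 80-minute gap has about 99% power.

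Severity: minor to should-fix. The primary outcome, the designated safety outcomes and the sample size are not undermined.

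**What to change.** Change no compression schedule, sample size or primary outcome.

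1. Make the between-arm comparison of bleeding, oozing and hematoma over one common window, from sheath removal to discharge or 24 hours as in the safety outcomes. Name that window for the SAP's hematoma outcome. Keep counts during TTH as description by arm, without a test.
2. Confirm that the case report form records oozing after deflation in both arms. Report time to discharge by arm, because the end of the window can differ.
3. Report the 40- and 60-minute TTH cut-offs by arm with the exact confidence intervals already planned and no between-arm p-value. State how hemostasis within one hour is timed; if by TTH, treat it the same way.
4. Word the TTH conclusion as disc with its schedule against band with its schedule. State that the 90% power refers to time to band removal.

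Cost: a few sentences in the protocol, SAP and report. Access-site events to discharge or 24 hours are already collected; a form item may be needed if later oozing is not recorded. Two threshold comparisons, or three if the one-hour outcome is timed by TTH, lose their p-values, and the TTH claim becomes narrower.

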A PROSPECTIVE RANDOMIZED STUDY COMPARING THE INCIDENCE OF RADIAL ARTERY OCCLUSION (RAO) AND THE TIME TO HEMOSTASIS (TTH) WHEN USING A HEMOSTASIS BAND ALONE AND IN CONJUNCTION WITH A DISC COMPRISED OF POTASSIUM FERRATE (STATSEAL ADVANCED) FOLLOWING TRANSRADIAL CATHETERIZATION. Study Sponsor: A Physician Initiated Study

Principal Investigator: [name], MPA

Cardiology Division Veterans Medical Center Long Beach

Statistical Analysis

Continuous data are presented as mean \pm standard deviation and as median [interquartile range], and compared using unpaired t-test and Mann-Whitney U-test, respectively. Discrete data are presented as frequencies with their respective percentages and compared using Fisher's exact test. Outcome data were analyzed on an intention-to-treat basis. Two-tailed tests of significance are reported and p values < 0.05 were considered statistically significant. Univariate logistic regression was performed using all baseline patient and procedural variables available to predict the secondary outcome of hematoma formation. Variables that were significant in univariate analysis at $p<0.25$ were retained and entered into a multivariate model with a threshold of $p<0.05$ being considered as significant. Statistical analyses were performed using the SPSS statistical software program (SPSS version 16.0.2, Chicago, IL).

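### The primary outcome, time to hemostasis, has two differing definitions, and neither says what value a patient who re-bleeds or has a complication receives

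*Protocol*

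**What the plan says.** - **Protocol, section III (Study Objectives), on the system:** "HMS is defined as the Hemostasis Management System employed based on which group the patient is randomized to (either SSA or TRB"). Compression by any other means is therefore not compression by the HMS.
- **Protocol, section III, on TTH:** "the time during which the subject is wearing the HMS system and the system is active, e.g. applying compressive force to the access site". It adds that "the time period that a HMS is left on the wrist while totally deflated is not considered as part of the TTH time". No condition on complications appears.
- **Protocol, section VI, Primary Efficacy Outcomes:** TTH is the "total time the HMS applies compressive force until successful hemostasis is achieved without complication".
- **Protocol, section VI, categorical variables:** one item is "Percent of patients in each arm with TTH of 40 minutes or less without complication"; another is a TTH of at most 60 minutes, with no such qualifier. A further item tabulates access-site bleeding and hematoma arising within the TTH period.
- **Protocol, section IV, treatment schedules:** in the disc arm (SSA) the band is fully deflated at 40 minutes and taken off at 60. In the control arm (TRB) it stays inflated for 2 hours, "after which deflation attempts will commence".
- **SAP, Statistical Analysis:** "Outcome data were analyzed on an intention-to-treat basis". The SAP does not define TTH and has no rule for a missing or incomplete value.

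**The concern.** The two definitions agree for a patient whose band is deflated once and whose site stays dry. They part company, or fall silent, for the patient whose first deflation fails.

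The section VI version has an end point that a patient with a complication does not literally reach. The term complication is not tied there to any list: elsewhere in section VI even class I or II hematoma is called a minor complication. In addition, both versions count only compression by the assigned system, so manual pressure or a different device adds nothing.

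The trial compares a short schedule with a long one, so what happens after deflation is what separates a true gain in time from an early release that has to be repeated. If sites or analysts fill the gap differently, the mean TTH and the percentage within 60 minutes depend on unrecorded choices. An intention-to-treat analysis needs a value for each randomized patient, and the plan gives no rule that supplies one here.

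**Working it through.** **1. The plan's own figure.** Inputs from Protocol section VI: difference 60 minutes, SD 100, two-sided alpha 0.05, power 90%, 120 patients (60 per arm, section IV). Per arm, n = 2 × (1.960 + 1.282)² × 100² / 60² = 2 × 10.51 × 2.778 = 58.4, so 59 per arm and 118 in total. With the t distribution, 60 per arm is the smallest number reaching 90% (power 0.903). The 120 reproduces; the sample size is not in question. The planned 60 minutes is stated for time to band removal, not for TTH, so below it serves only as a yardstick.

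**2. One patient, three readings.** Take a patient who re-bleeds after the first full deflation and needs X more minutes of compression. Scheduled active time is 40 minutes for SSA and at least 120 for control. X = 30 or 60 is an assumption.

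| Reading | SSA, X = 30 | SSA, X = 60 | Control, X = 30 | Control, X = 60 |
|---|---|---|---|---|
| Same band re-inflated, time added | 70 | 100 | 150 | 180 |
| Rescue by hand or another device, or clock stopped at first full deflation | 40 | 40 | 120 | 120 |
| Complication treated as barring a value | none | none | none | none |

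The visible text does not choose between the rows.

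**3. Effect on the mean.** If a share f of one arm has X uncounted minutes, that arm's mean is understated by f × X.
- f = 0.10, X = 30: 0.10 × 30 = 3 minutes.
- f = 0.20, X = 60: 0.20 × 60 = 12 minutes.
- On schedule the counted SSA mean is 40, where the full figure would be 43 to 52. The gap to 120 is 77 to 68 minutes instead of 80.
- Wider range, f = 5–30% and X = 20–120: from 0.05 × 20 = 1 to 0.30 × 120 = 36 minutes. The scheduled gap of 80 becomes 79 to 44, still in the same direction.
- If both arms have failures, the bias in the difference is f(SSA) × X(SSA) − f(control) × X(control), which is zero when the two products are equal.

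**4. Effect on the 60-minute percentage.** In the SSA arm any X above 20 takes total compression past 60 minutes (40 + 20).
- Failures dropped: if a share s of the other patients meets the cutoff, the percentage reported is s instead of s × (1 − f). The overstatement is s × f, at most f.
- Failures scored at 40: the overstatement is f.
- With f = 10–20%, that is up to 10–20 percentage points, or 6–12 of 60 patients.
- A control patient on schedule has at least 120 minutes and misses the cutoff under any reading, so the distortion falls on the SSA percentage.

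**5. The 40-minute item.** It carries its own complication-free condition within each arm. A patient with a complication counts as not meeting it, so it penalizes failures.

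**6. Power, for scale.** If the counted difference were 60 minutes and 3–12 minutes of SSA compression went uncounted, the difference in all compression would be 57–48. At 60 per arm and SD 100 (normal approximation), power is 0.908 for 60, 0.877 for 57 and 0.748 for 48.

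**The case against.** The best defense is that the plan can be read sensibly. Total time until successful hemostasis can be cumulative: a patient who re-bleeds has not yet succeeded, and re-inflating the band lengthens TTH. Two items in section VI, bleeding within the TTH period and the qualified 40-minute percentage, presuppose that patients with complications have a TTH. The only stated exclusion is withdrawal of consent (section IV). Access-site bleeding and hematoma are safety outcomes, so failures are not hidden. Section II says that earlier testing of the disc found no more complications than standard methods. The CRFs and the study graphic are not in the text available, and a recording rule there cannot be excluded.

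Most of this stands, and it rules out several stronger conclusions that a reader might draw:

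- *Failures are always shortened or dropped, in favor of the disc.* No text prescribes this, and re-inflation can work the other way.
- *The 40-minute percentage flatters the arm with more failures.* Its own wording does the reverse.
- *The SAP's intention-to-treat statement is contradicted.* No rule removes failed patients. The difficulty is that none gives them a value.
- *The result could reverse.* Nothing shows that, with 40 scheduled minutes against at least 120.

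The defense does not remove the core point. The items implying that complicated patients have a TTH disagree with the literal primary definition, which is a reason to reconcile them. Cumulative reading helps only when the rescue is the assigned band; other compression remains uncounted in both sections.

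**Conclusion.** The point holds as a conflict and a gap in the definition of the primary outcome, not as a demonstrated bias. Sections III and VI differ on the complication condition, both omit compression outside the assigned system, and the value for a patient who re-bleeds or has a complication may be lengthened, shortened or missing.

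The size cannot be taken from the documents, which give neither a failure rate nor a rescue duration. Under the stated assumption (10–20% of one arm, 30–60 minutes, all uncounted) that arm's mean is 3–12 minutes too low and the SSA 60-minute percentage up to 10–20 points too high. Failures in the other arm, or rescue by the assigned band, would reduce the bias. Against a scheduled gap of 80 minutes, the estimate and the 60-minute percentage are at risk more than the direction. The sponsor should correct it; it does not threaten the trial as a whole.

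**What to change.** Use one definition of TTH in Protocol sections III and VI, and repeat it in the SAP: total minutes of active compression at the access site by any method (assigned band, re-inflation, manual pressure or another device), leaving out time when the band is totally deflated, up to final hemostasis before discharge or 24 hours.

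- Delete the complication condition from the primary definition.
- Compute TTH for every randomized patient who has not withdrawn.
- Report complications, and the percentage needing any re-compression, separately by arm.

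The measure should stay cumulative. Elapsed time from sheath removal to the last compression would contradict section III, which excludes deflated time, and one brief late ooze would inflate the value out of proportion.

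This is a measurement rule and changes no patient's care. It costs a wording change, start and stop times for any re-compression on the CRF, and slightly less favorable TTH values.
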